## Appendix 8: Details of the historical HSCT control group

### 1. Objective

Historical data from ADA-SCID patients who were treated with Hematopoietic Stem Cell Transplantation (HSCT) at GOSH during the period of 2000-2016 will be collected. HSCT is currently the standard of care for ADA-SCID patients. These data will be used as historical control group in a current on-going gene therapy study “Phase I/II, historical controlled, open-label, non-randomised, single-centre trial to assess the safety and efficacy of EF1αS-ADA lentiviral vector mediated gene modification of autologous CD34+ cells from ADA-deficient individuals”. The objective is to compare efficacy and safety of gene therapy versus HSCT to determine the optimal treatment.

### 2. Study population

The control group will be patients from 0-18 years of age with a confirmed diagnosis of ADA deficiency transplanted at Great Ormond Street Hospital (GOSH) since 2000. See inclusion criteria page 64.

### 3. Data to be collected

GOSH holds a registry / clinical database (European Society for Immunodeficiencies (ESID) and European Society for Blood and Marrow Transplant (EBMT) Registry, GOSH BMT clinical database) displaying information on these types of patients. Patients treated with HSCT have been identified who received a transplant at GOSH between 2000-2016. . ESID and EBMT will allow us to collect the below information:

- Demographics (gender, date of birth, date of death if any),
- Method of ADA-SCID diagnosis,
- HSCT treatment(s) including: date of treatment, transplant cells, donor type and outcome

However, to make this historical control group valid for marketing authorisation application, our discussions with regulatory agencies suggests that we need to collect further information valuable to compare the efficacy and safety of any new treatment in research vs. current HSCT standard of care as:

- Previous PEG-ADA ERT (and duration of treatment),
- Previous or current immunoglobulin therapy,
- Listing of relevant medical history, including infections (severe or opportunistic infections)
- Vaccination history and immunological response to vaccination

- Auto-immune disease
- Malignant disease / leukaemia
- Graft versus host disease
- ADA activity and ADA metabolites
- AEs and SAEs

This information is only available from the patient's records; we therefore plan to re-consent these patients to access their full medical records.

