#### **4. Data collection process**

This is a retrospective, non-interventional data collection activity; the patients follow their routine medical practice. We will contact these patients or their authorised representative and seek their consent to access their medical notes and share the information with regulatory agencies and pharmaceutical companies involved with the licensing process. HSCT historical control group data team will work on the collection of data from GOSH registries and patients' records, data will be entered into an electronic Case Report Form (eCRF). This eCRF will be monitored as per standard process before it can be used for statistical analysis and submission to agencies for review and assessment.

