### **8.1 Subject Disposition**

#### **8.1.1 Summary of Populations**

Number (%) of subjects enrolled (signed informed consent), treated, and in efficacy and safety populations will be summarised for the IMP treated and HSCT control groups. The denominator for the percentages will be the number of subjects enrolled.

Should any subjects be excluded from any of the analysis populations, a listing will be produced for these subjects noting the reason for exclusion.

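### SAP 8.1.1 counts the transplant controls by signed consent while SAP 7.1 and 7.2 define them by treatment, and no rule covers children who died, untraced families or refusals, so consent-related selection of controls is not excluded

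*Protocol*

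**What the plan says.** Appendix 8 of the protocol, section 3, describes two layers of control data.

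- **Registry layer.** The cohort is already known: "Patients treated with HSCT have been identified who received a transplant at GOSH between 2000-2016". The registry items include "Demographics (gender, date of birth, date of death if any", the method of diagnosis, and "HSCT treatment(s) including: date of treatment, transplant cells, donor type and outcome".
- **Medical-record layer.** A second list covers previous PEG-ADA, immunoglobulin therapy, infections, vaccination, graft versus host disease, ADA activity and metabolites, AEs and SAEs. The protocol says these can be had only from the notes, and continues: "we therefore plan to re-consent these patients to access their full medical records".

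Section 4 of the same appendix adds: "We will contact these patients or their authorised representative and seek their consent to access their medical notes". The same consent is to cover passing information to regulators and companies. The control eCRF is to be filled from both registries and patient records.

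The SAP then treats the cohort in two ways.

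- **Section 8.1.1:** the number and percentage "enrolled (signed informed consent), treated, and in efficacy and safety populations will be summarised for the IMP treated and HSCT control groups". The enrolled count is the denominator for those percentages.
- **Sections 7.1 and 7.2:** the control populations are set by diagnosis, donor availability, and transplant at this site from 2000. The cohort with any donor type is described as complete. Consent is not a criterion.

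Protocol 5.3 agrees with 7.1 and 7.2. It has three control criteria (diagnosis, age, transplant since 2000) and consent is not among them. Protocol 5.1.1 does list signed consent for on-trial patients.

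**The concern.** The historical HSCT group is the only comparator for overall and event-free survival. The transplant window runs from 2000 to 2016, so for the earliest cases consent is sought some 16 years after transplant. Whether a family can be traced and agrees may be related to whether the child survived or the graft failed. If the analysed controls are only those with signed consent, the control estimates are conditioned on something that may depend on outcome.

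Nothing in the plan would bring this to light. SAP 8.3.1.1 deals only with subjects who withdrew before 12 months. SAP 8.3.4 is triggered only by protocol violations. SAP 8.1.1 does ask for a listing, with reasons, of subjects left out of an analysis population. But a control who never consented was never enrolled under that section's own definition and need not appear. Neither document asks how many controls were identified, contacted, consented, declined or untraced.

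**Working it through.** The plan states no control number, consent rate or power, so there is no design figure to reproduce.

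**Step 1. Compare the definitions.** SAP 8.1.1 expresses the efficacy and safety populations as percentages of consented subjects. That works only if every analysed control consented. SAP 7.1, 7.2 and Protocol 5.3 admit controls without reference to consent. If some analysed controls did not consent, the 8.1.1 percentages could exceed 100%. If all did, the cohort called complete may not be complete.

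**Step 2. Which outcomes depend on consent?**

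| Outcome | Source listed in Appendix 8 |
|---|---|
| Death, transplant date, donor type | Registry |
| Second transplant | Registry treatment entries, apparently |
| Date last known alive | Not listed |
| Return to PEG-ADA after transplant | Not listed as a registry field; the record list names previous PEG-ADA only |
| Immunoglobulin therapy, infections, SAEs | Medical records, hence re-consent |

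SAP 8.3.1.2 counts death, reinstitution of PEG-ADA and a second transplant as events. At least one component of event-free survival is therefore not secured by the registry list.

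**Step 3. Size, by assumption.** Protocol 5.1.3 gives 67% survival in 15 matched-unrelated-donor transplants, that is 10 of 15. Let *a* be the consent rate for survivors and *b* the rate for families of children who died; the documents give neither. Apparent survival is 10a / (10a + 5b).

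- a = 0.9, b = 0.5: 9.0 / (9.0 + 2.5) = 78.3%, or +11.6 points
- a = 0.8, b = 0.3: 8.0 / (8.0 + 1.5) = 84.2%, or +17.5 points
- a = 0.6, b = 1.0: 6.0 / (6.0 + 5.0) = 54.5%, or -12.1 points
- a = b = 0.9: 9.0 / (9.0 + 4.5) = 66.7%, no bias

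The shift also depends on true survival S, through S·a / (S·a + (1 - S)·b). Protocol 3.2.1 reports 43% for haploidentical and 86% for matched sibling donors. With a = 0.9 and b = 0.5:

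- S = 0.43: 0.387 / (0.387 + 0.285) = 57.6%, or +14.6 points
- S = 0.86: 0.774 / (0.774 + 0.070) = 91.7%, or +5.7 points

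**Step 4. How few families matter.** If *u* of the assumed 15 are not included, apparent survival lies between (10 - u)/(15 - u) and 10/(15 - u).

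- u = 2: 8/13 to 10/13, 61.5% to 76.9%
- u = 3: 7/12 to 10/12, 58.3% to 83.3%
- u = 5: 5/10 to 10/10, 50.0% to 100%

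Against an assumed 10 of 10 gene-therapy survivors, the difference is 33.3 points with all 15 controls. It is 16.7 points if three deaths are missing (10/12) and 45.5 points if four survivors are missing (6/11).

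**Step 5. What bounds would show.** Keep all 15 in the denominator and count the *u* unknowns first as all failures, then as all successes. The interval is u/15 wide: 13.3 points for u = 2, 20.0 for u = 3, 33.3 for u = 5. For event-free survival it narrows if registry data already show a death or second transplant by the time point, since those children are known failures.

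**The case against.** The strongest reply is that the current text leans towards full inclusion. The population definitions carry no consent condition, the children are already identified, the dates of death and transplant are listed as registry data, and registries are named as a source separate from the notes. SAP 8.1.1 is a disposition table, and its loose wording, shared by both arms, does not override the populations used for the survival analyses. This stands. A reader might infer that control overall survival is restricted to families who could be reached. The documents do not say so, and overall survival may already be intended for every transplanted child.

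The opposite inference, that registry data settle overall survival for everyone, also goes too far. The registry list gives no date of last contact, while SAP 8.3.1.1 censors at last evaluation. SAP 8.2.16 takes control follow-up from the eCRF without naming its source. The consent in Appendix 8 also covers sharing, so use of non-consenters' registry data in this submission is not settled.

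A third inference is that return to PEG-ADA is recorded only in the notes. That is plausible, but Appendix 8 does not place it on either list, and the registry outcome item is not defined.

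The sizing also has limits. The consent rates are assumed. The 10 of 15 comes from a multicentre matched-unrelated-donor series, whereas the primary control group is this site's patients without a matched family donor, whose number and survival are not given. Nothing in the documents shows that bereaved families respond differently. Finally, the protocol calls the comparison descriptive, but selection shifts a descriptive estimate as much as a tested one.

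**Conclusion.** The point holds as an unresolved inconsistency and a missing rule. SAP 8.1.1 does not fit SAP 7.1, 7.2 and Protocol 5.3, and neither document handles controls who died, cannot be traced or decline. Selection by consent is not excluded for overall survival. It is likely for outcomes that rest on medical records: immunoglobulin use, infections, SAEs and, through PEG-ADA after transplant, event-free survival.

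Neither direction nor size can be determined from the documents. The range of about 55% to 84% around 67% rests on an assumed cohort and assumed unequal consent rates. It shows only that a handful of missing families could matter in a group of this size. It does not show that the comparison is biased, or that any bias favours gene therapy. The matter should be settled because this is the only comparator and the remedy is cheap.

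**What to change.** 1. In SAP 8.1.1, change the control denominator to all eligible transplants identified in the registries, in line with 7.1 and 7.2. Say explicitly whether consent is a condition for any control analysis.
2. Where data permissions allow, compute control overall survival and second transplant from registry data for every identified eligible transplant, censoring at last known contact. Where they do not, report best- and worst-case bounds for those not included.
3. Add a table of controls identified, contacted, consented, declined and untraced, by donor type and, where permitted, vital status.
4. Report control event-free survival for those with records, with best- and worst-case bounds for the rest.

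The cost is SAP wording, one table and a little extra analysis. The stated uncertainty for the control group will be wider. The sponsor must also confirm that registry data may be used without re-consent and obtain a last-contact date, which is not among the listed registry items.

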#### **4. Data collection process**

This is a retrospective, non-interventional data collection activity; the patients follow their routine medical practice. We will contact these patients or their authorised representative and seek their consent to access their medical notes and share the information with regulatory agencies and pharmaceutical companies involved with the licensing process. HSCT historical control group data team will work on the collection of data from GOSH registries and patients' records, data will be entered into an electronic Case Report Form (eCRF). This eCRF will be monitored as per standard process before it can be used for statistical analysis and submission to agencies for review and assessment.

#### **5. Data Analysis**

The comparison analysis between gene therapy and HSCT will be performed evaluating data related to:

Survival and event free survival, defined as need to return to PEG-ADA or second transplant at 1 and 2 years post treatment.

Use of immunoglobulin replacement therapy (IgRT) and infections post treatments. Infections are defined as infections requiring hospitalisation or prolonging hospitalization and/or documented infections by opportunistic pathogens (interstitial pneumonia, intractable diarrhoea)

## **Appendix 9: Details of the CUP group**

Great Ormond Street Hospital holds a Specials License from the MHRA for the manufacture of gene modified products for compassionate use. This license allows a physician to treat a patient with an unlicensed product in case of a special need. These ADA-SCID patients treated under this Special License could not be enrolled into the clinical trial for various reasons: the trial was not yet opened and patients were in clinical need of treatment; the patient could not meet the inclusion/exclusion criteria; the final formulation of the product was different (cryopreserved instead of fresh transduced cells); the product could not meet the release specification, the trial recruitment was already completed and patients were in clinical need of treatment.

However, in the treatment of these patients we have applied similar standards to clinical trial i.e. the patient gives their consent to collect data, the same trial monitoring schedule/trial procedure is applied, and pharmacovigilance (SAE) is documented in the same way. These patients will be included part of the analysis for the safety and secondary efficacy objectives only as mentioned in section 8.9.

## List of Abbreviations

ADA	Adenosine deaminase
ADA-SCID	Adenosine deaminase severe combined immunodeficiency
AE	Adverse event
ALT	Alanine aminotransferase
APT	Activated partial thromboplastin
AST	Aspartate aminotransferase
AUC	Area under the curve
BM	Bone marrow
BSA	Body surface area
CI	Confidence interval
CMV	Cytomegalovirus
CUP	Compassionate use programme
dATP	Deoxyadenosine triphosphate
DNA	Deoxyribonucleic acid
EBV	Epstein-Barr virus
ECG	Electrocardiogram
eCRF	Electronic case report form
EFS	Elongation Factor 1 $\alpha$ Short form
ERT	Enzyme replacement therapy
G-CSF	Granulocyte-colony stimulating factor
GFR	Glomerular filtration rate
GGT	Gamma glutamyl transferase
GOSH	Great Ormond Street Hospital
HIV	Human immunodeficiency virus
HLA	Human leukocyte antigen
HSC	Hematopoietic stem cell
HSCT	Hematopoietic stem cell transplant
HSV	Herpes simplex virus
HTLV	Human T-lymphotropic virus
Ig	Immunoglobulin
IgA	Immunoglobulin A
IgG	Immunoglobulin G
IgM	Immunoglobulin M
IgRT	Immunoglobulin replacement therapy
IMP	Investigational medicinal product
LV	Lentiviral vector
MCH	Mean corpuscular haemoglobin
MCHC	Mean corpuscular haemoglobin concentration
MCV	Mean corpuscular volume

MedDRA	Medical Dictionary for Regulatory Activities
MMRM	Mixed model for repeated measures
MNC	Mononuclear cells
NK	Natural Killer
PBMC	Peripheral blood mononuclear cells
PBSC	Peripheral blood stem cells
PCR	Polymerase chain reaction
PEG	Polyethylene-glycol
PHA	Phytohemagglutinin
PI	Principal Investigator
PT	Preferred Term
qPCR	Quantitative polymerase chain reaction
RBC	Red blood cell(s)
RCL	Replication competent lentivirus
SAE	Serious Adverse Event
SAP	Statistical analysis plan
SCID	Severe combined immunodeficiency
SCLN	Save cells in liquid nitrogen
SOC	System Organ Class
TCR	T-cell receptor
TREC	T-cell receptor excision circle
UK	United Kingdom
VZV	Varicella zoster virus
WBC	White blood cell(s)

## 1 Introduction

The trial assesses a new breakthrough therapy composed of *ex vivo* genetically modified CD34+ hematopoietic stem cells (HSC) for the treatment of severe combined immunodeficiency due to adenosine deaminase deficiency (ADA-SCID).

The investigational medicinal product (IMP) includes autologous CD34+ HSC of ADA-SCID infants, children and adolescents, transduced *ex vivo* with a self-inactivating HIV-1 based lentiviral vector encoding the human ADA cDNA (EFS-ADA LV). The IMP is used as fresh cell dispersion for infusion after non-myeloablative conditioning.

## 2 Study Design

This is a Phase I/II, historical controlled, open-label, non-randomised, single-centre trial to assess the safety and efficacy of the IMP, i.e. autologous CD34+ HSC transduced *ex vivo* with EFS-ADA LV in ADA-SCID patients.

The IMP will be compared with an historical control group treated with allogeneic Hematopoietic Stem Cell Transplantation (HSCT), representative of standard of care.

The study is conducted in a single centre at Great Ormond Street Hospital (GOSH) for Children, London, UK.

### **3 Study Schedule**

	Visit window	PreGT	Treatment	Timepoint (months) ^											
				+/- 5d	+/- 5d	+/- 2w									
Assessment	Parameter to be reported on the eCRF			1	1.5	3	6	9	12	18	24	30	36		
Inclusion / Exclusion criteria	-	X													
Pregnancy test for patient >12 years old	-	X*													
Diagnosis	DNA sequencing (mutation, exon, polymorphism) OR Confirmed absence of <3% enzymatic activity	X													
Medical history	Infection/hospitalisation history Transplantation history	X													
Coagulation testing	PTT, APT, Thrombin Time, Fibrinogen	X													
Blood ABO testing	Determination, Rhesus	X													
Extended B cell memory	CD19 Naïve B cells CD19+IgD+CD27- Non Switched memory B cells CD19+IgD+CD27+ Class Switched memory B cells CD19+IgD-CD27+ Transitional B cells CD19+IgM++CD38++ Plasmablasts CD19+CD38++IgMwk CD21 low B cells CD19+CD21wkCD38wk	X									X		X		X
Virology	CMV, EBV, Adenovirus, HIV1, HIV2, VZV, Hep A, Hep B, HSV, Hep C, Syphilis, HTLV1, HTLV2, Toxoplasma	X													
Biochemistry	Sodium, Potassium, Urea, Creatinine, Calcium, Magnesium, Phosphate, Albumin, Alkaline Phosphatase (ALP), Alanine Transaminase(ALT), gamma-glutamyltranferase(GGT), Bilirubin	X		X	X	X	X	X	X	X	X	X	X	X	X
Glomerular Filtration	Weight, Creatinine, Distribution volume, Half-life Glomerular Filtration, corrected GFR	X													
Chest x-ray	Normal/Abnormal	X													
ECG	Normal/Abnormal	X													
Echocardiogram	Normal/Abnormal	X													
Lung function test if applicable\\	Normal/Abnormal	X													
Dental	Normal/Abnormal	X													
Audiology	Normal/Abnormal	X													
Maternal engraftment studies	Normal/Abnormal	X													

Assessment	Result to be reported on the eCRF	PreGT	Treatment	1	1.5	3	6	9	12	18	24	30	36
Back-up harvest	Harvest type BM or leukapheresis, CD34+cell count		X										
Harvest for IMP preparation	If leukapheresis : Mobilisation: G-CSF (date dose) +/- Plerixafor (date, dose), Leukapheresis harvest: patient's weight, date, CD34+cell dose for transduction If BM: patient's weight, date, CD34+cell dose for transduction)		X										
Conditioning	Patient weight, Busulfan dose, Busulfan AUC		X										
IMP administration	Infusion date, IMP expiry, IMP start date, IMP end date, IMP cell dose, IMP viability, IMP volume Observation before, +15min, after infusion		X										
Vital Signs	Patient's weight Temperature Heart rate Respiratory rate Oxygen saturation	X	X	X	X	X	X	X	X	X	X	X	X
Physical examination	Cardiovascular system Respiratory system Ear, Nose, Throat, Neck and Eyes (only at PreGT, 36 m) Neurological System (only at PreGT, 36 months) Abdominal Skin Other	X		X	X	X	X	X	X	X	X	X	X
Infection status	Evaluate any active infection at time of visit (respiratory tract, meningitis, sepsis, skin and mucosa, ear, nose and throat, abscess, persistent fever, other) Evaluate if there is any infection resulting in hospitalisation since last visit	X		X	X	X	X	X	X	X	X	X	X
PEG-ADA ERT status	Confirmation that if PEG-ADA has been administered or not since last visit	X		X	X	X	X	X	X	X	X	X	X
Blood Count	Haemoglobin, Platelet count White cell count Neutrophil count Lymphocyte count	X		X	X	X	X	X	X	X	X	X	X

Assessment	Result to be reported on the CRF	PreGT	Treatment	1	1.5	3	6	9	12	18	24	30	36
Lymphocyte subset counts	CD 3 CD19 CD16+ CD 56+ CD3+ CD4+ CD3+ CD8+ Naïve: CD4+CD45RA+CD27+	X		X	X	X	X	X	X	X	X	X	X
T cell function PHA stimulation**	Normal/Abnormal	X				X	X		X	X	X		
Lymphocyte function CD3 stimulation**	Normal/Abnormal								X			X	
GAM ***	Ig G level Ig A level Ig M level Immunoglobulin status since last visit	X						X	X	X	X	X	X
TRECS	TRECS on T cells TRECS on MNCs	X						X		X		X	
Vβ Spectratyping	Reported as Normal/Abnormal							X		X	X	X	X
Vector copy number in cells (qPCR)	vector copy number in PBMC vector copy number in CD34 vector copy number in CD3 vector copy number in CD19 vector copy number in myeloid						X	X		X		X	
Integration analysis	Normal/Abnormal						X****	X****		X		X****	X
Tetanus vaccination responses	Normal/Abnormal											X	X
ADA metabolite analysis (dATP) and ADA activity	Plasma deoxyadenosine level ADA (rbc) level dATP level	X		X	X	X	X	X	X	X	X	X	X
RCL (blood)	Reported as detectable / not detectable	X				X****	X****		X		X****		X

Assessment	Result to be reported on the CRF	PreGT	Treatment	1	1.5	3	6	9	12	18	24	30	36
Bone marrow aspirate for vector copy number qPCR and integration analysis (optional)	Morphology (Normal/ Abnormal) Vector copy number in BM-MNC Integration analysis (Normal / Abnormal)								X		X		X
Immunology save serum & SCLN (stored cells)	Serum collection date SCLN s collection date	X						X		X	X	X	X
Reporting of Adverse Event			X	X	X	X	X	X	X	X	X	X	X
Reporting of Concomitant Treatment ^^			X	X	X	X	X	X	X	X	X	X	X

^Lab results to be entered into eCRF for these time points should be the ones closer to the consent date/ visit date

^^ Concomitant reporting: In case of any change in administering a concomitant medication i.e. dose, frequency etc. the previous medication should be stopped where the new medication has started

\* Assay to be performed only if patient > 12 years of age

\*\* Assay can only be performed if the lymphocyte count > 0.5 x 10^9/L

